### **10.2.3 Treatment-Emergent Adverse Events by SOC and/or PT**

Treatment-emergent adverse events will be summarized by SOC and PT; by maximum relationship to study drug as assessed by the investigator (e.g., reasonable possibility or no reasonable possibility) and SOC and PT; by maximum severity and SOC and PT; and by subject number and SOC and PT. Specific adverse events will be counted once for each subject for calculating percentages, unless stated otherwise. In addition, if the same adverse event occurs multiple times within a subject, the highest severity and level of relationship to investigational product will be reported.

In addition, treatment-emergent adverse events will be summarized by PT and sorted by decreasing frequency for the total active group.

#### **10.2.4 Treatment-Emergent Adverse Events per Patient-Years of Exposure**

Exposure-adjusted AEs per 100 patient-years will be provided, where AEs per 100 patient-years of exposure are defined as the number of AEs divided by the total exposure in 100 patient-years. The study drug exposure is defined as the last dose date plus  $5 \times$  half-life (70 days), minus the first dose date.

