5.6 Follow-Up After Subject Discontinuation of Study Drug or from Study

Discontinuation of Study Drug and Continuation of Study Participation

To minimize missing data for efficacy and safety assessments, subjects who prematurely discontinue study drug treatment should be encouraged to continue to be followed for all regularly scheduled visits (except for visits that are intended only for study drug administration [Weeks 6, 10, 14, 18, 22, 26, 30, 34, 38, 42, 46, and 50]), unless the subject has decided to discontinue the study participation entirely (withdrawal of informed consent). At the visits after study drug discontinuation, subjects should adhere to all study procedures except for dispensing of study drug and accountability, dosing diaries, and PK (conjugated ADC, total antibody, free A-1677770 assays) and immunogenicity (ADA assays) sample collection. Subjects should be advised on the continued scientific importance of their data even if they discontinue treatment with study drug early. Following discontinuation of study drug, the subject should be treated in accordance with the investigator's best clinical judgment irrespective of whether the subject decides to continue participation in the study.

If a subject prematurely discontinues study drug, the procedures outlined for the Premature Discontinuation Visit should be completed as soon as possible, preferably within 2 weeks, and preferably prior to initiation of another therapy.

In addition, a 30-day Follow-up Phone Call and 70-Day Follow-up Visit after the last dose of study drug is required to ensure all treatment-emergent AEs/SAE have been resolved. All attempts must be made to determine the date of the last study drug dose and the primary reason for discontinuation of study drug or study participation. This information will be recorded on the appropriate eCRF page. This Follow-up

Phone Call is not applicable for subjects who discontinued study drug prematurely and continued study participation with completion of at least 1 study visit that was at least 30 days after the last dose of study drug. This visit is not applicable for subjects who discontinued study drug prematurely and continued study participation with completion of at least 1 study visit that was at least 70 days after the last dose of study drug.

Premature Discontinuation of Study (Withdrawal of Informed Consent)

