7.5 Statistical Analyses for Safety

All safety analyses will be performed using the Safety Population, as defined in Section 7.2. Data will be analyzed based on the actual treatment subjects received. TEAEs, laboratory assessments, and vital signs will be summarized. Details will be described in the SAP.

A TEAE for the Safety Population is defined as an AE newly occurred or worsened after the first dose of study drug and within 70 days after the last dose of study drug. The number and percentage of subjects experiencing TEAEs will be tabulated using the Medical Dictionary for Regulatory Activities (MedDRA) system organ class and preferred term, by severity, and by relationship to the study drug as assessed by the investigator. Summaries (including percentages and events per 100 patient years) of SAEs, deaths, and AEs leading to discontinuation will also be provided. Pretreatment AEs will be summarized separately.

For selected laboratory parameters, a listing of all subjects with any laboratory value that is Grade ≥ 3 of NCI CTCAE will be provided. Mean change in laboratory and vital signs variables will be summarized. Additional details for the safety analysis are provided in the SAP.

[figure not shown]

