## 2.2 Study Design Overview

Study M20-370 is a randomized, double-blind, placebo-controlled, multicenter, 52-week Phase 2 study to assess the safety, tolerability, efficacy, PK, PD, and immunogenicity following multiple subcutaneous (SC) injections of ABBV-154 or placebo in 160 subjects with glucocorticoid-dependent PMR, as defined in Section 5.0.

The Primary Analysis will be performed after all subjects have either completed the Week 24 visit or withdrawn from the study. Interim analyses may be performed to reassess the treatment regimens in this study and to inform development of future studies.

A final analysis will be conducted after all subjects have either withdrawn from the study or completed Week 52 and the safety Follow-up Visit. To maintain integrity of the trial, the study sites and subjects will remain blinded until the final analysis is completed. Selected AbbVie personnel may be unblinded to treatment assignment to conduct interim

[figure not shown]
analyses or after an interim analysis to support regulatory interaction; details will be included in the interim unblinding plan (IUP).

Subjects in select countries and sites where the digital health technology device is deployed and available will also participate in a Wearable Device Substudy. Subjects participating in this substudy will wear a watch-like digital device on the wrist that will collect data reflecting the subject's UL-ROM and daily activity and sleep parameters. Enrollment will be capped at 96 subjects.

There will be optional serial photography for subjects who consent and at sites where photography is available.

The schematic of the study is shown in Figure 1.

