### **10.2.1 Treatment-Emergent Adverse Events**

Treatment-emergent AEs are defined as any AE with the onset that is after the first dose of study drug and with an onset date no more than 5 half-lives of the study drug (i.e., 70 days). Events where the onset date is the same as the study drug start date are assumed to be treatment-emergent, unless the study drug start time and the AE start time are collected and the AE start time is prior to the study drug start time. All treatment-emergent AEs will be summarized overall, as well as by primary MedDRA SOC and Preferred Term. The SOCs will be presented in alphabetical order, and the PTs will be presented in alphabetical order within each SOC.

The number and percentage of subjects experiencing treatment-emergent AEs will be summarized.

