## **12.0 Interim Analyses**

An interim analysis will be conducted for this study approximately 3 weeks before the Primary Analysis for M20-466 (ABBV-154 Rheumatoid Arthritis [RA] Phase 2b study). Additional interim analyses may be performed to reassess the treatment regimens in this study and to inform development of future studies. The interim analysis result will not be reviewed by the Data Monitoring Committee (DMC).

A separate interim unblinding plan will be developed to describe the detailed interim analysis plan, including the interim unblinding team, decision rules, execution logistics, and data chain of custody to protect the integrity of the clinical study. The interim analysis result will not be reviewed by the Data Monitoring Committee (DMC) and the interim analysis plan will not be documented in the DMC charter.

These interim analyses will not impact the study conduct.

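### SAP 10.2.4 adds 70 days of exposure after the last dose with no cap at data cutoff, death or study exit, so rates per 100 patient-years are too low wherever that time is unobserved

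*SAP*

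**What the plan says.** SAP 10.2.4 gives the whole denominator in one sentence: "The study drug exposure is defined as the last dose date plus" five times the "half-life (70 days), minus the first dose date". Rates "are defined as the number of AEs divided by the total exposure in 100 patient-years". The same rates are planned for the adverse-event overview (10.2.2), for SAEs and events leading to discontinuation (10.2.5) and for events of special interest (10.2.6).

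The 70 days mirror the treatment-emergent window. Protocol 7.5 sets that window at "within 70 days after the last dose of study drug". SAP 10.2.1 words it as "with an onset date no more than 5 half-lives of the study drug (i.e., 70 days" and does not say that the count starts at the last dose.

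Three other passages decide when the 70 days are actually observed:
- SAP 2.2: "The Primary Analysis will be performed after all subjects have either completed the Week 24 visit or withdrawn from the study". Dosing continues to Week 50 (Protocol 5.8), so subjects may still be on treatment at that point.
- SAP 12.0: "An interim analysis will be conducted for this study approximately 3 weeks before the Primary Analysis for M20-466". Further interims are possible.
- Protocol 5.6, for subjects who stop drug but stay in the study: "a 30-day Follow-up Phone Call and 70-Day Follow-up Visit after the last dose of study drug is required". The visit is waived if another study visit takes place at least 70 days after the last dose. After withdrawal of consent the protocol asks only for a Premature Discontinuation visit, preferably within 2 weeks.

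The only cutoff rule in the SAP is the censoring rule for efficacy time-to-event endpoints (9.1). The product safety SAP is cited for events of special interest and for potentially clinically important criteria, not for exposure.

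**The concern.** The 70-day credit is not itself an error, because it matches the window in which events are counted. The problem is that event counting stops when observation stops and the denominator does not. Time in which nothing could be recorded can only lower the rate.

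This happens in two situations. The first is any data cut taken while subjects are on treatment or within 70 days of their last dose. The second is the final analysis, for subjects who die or leave the study within 70 days of their last dose. In the second case the arm with more early loss receives more unobserved time and looks slightly safer than it is. Safety is part of the primary objective, so the rates should not carry a built-in bias in that direction.

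**Working it through.** The documents state no total exposure and no event rate, so there is no planned figure to reproduce. The check compares credited with observable exposure.

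**From the documents.** Credited exposure S = last dose day + 70, counted from the first dose (SAP 10.2.4). Dosing is every 14 days, with the last dose at Week 50, or 350 days (Protocol 5.8). The Primary Analysis follows once the last subject reaches Week 24, or 168 days (SAP 2.2).

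**Assumed, because the documents give no figures.** Accrual period, adherence and loss from the study.

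**Formula.** Observable exposure O = min(S, days from first dose to cutoff, death or exit). With the event count fixed, the rate is too low by 1 − O/S.

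**Single subjects**
- Completer at the final analysis: S = 350 + 70 = 420 and O = 420, so no bias.
- On schedule at a cutoff: the last dose was 0 to 14 days earlier, so 56 to 70 credited days are unobserved (mean 63). If dosed on a Week 24 cutoff day, S = 238, O = 168, and 1 − 168/238 = 29.4%.
- Leaves 14 days after a single dose: S = 70, O = 14, and 1 − 14/70 = 80%.

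**Final analysis.** Assume leavers exit evenly over Days 0 to 364 and are dosed on schedule until exit. Mean O = 182, mean last dose = 182 − 7 = 175, and mean S = 175 + 70 = 245. All others have 420 for both. For loss p, S/O = [245p + 420(1 − p)] / [182p + 420(1 − p)].

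| Loss p | Mean S | Mean O | S/O | Rate too low by |
|---|---|---|---|---|
| 5% | 411.25 | 408.1 | 1.0077 | 0.8% |
| 10% | 402.5 | 396.2 | 1.0159 | 1.6% |
| 20% | 385.0 | 372.4 | 1.0338 | 3.3% |
| 30% | 367.5 | 348.6 | 1.0542 | 5.1% |

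If all exits fall before Week 24, mean O = 84 and mean S = 84 − 7 + 70 = 147. At 30% loss S/O = 338.1/319.2 = 1.059, and the rate is 5.6% too low.

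Between arms, 30% against 10% loss shifts the rate ratio by 1 − 1.0159/1.0542 = 3.6%. For 20% against 10% the shift is 1 − 1.0159/1.0338 = 1.7%.

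**Primary Analysis, if rates are tabulated then.** Assume uniform accrual over A weeks, cutoff at A + 24 weeks, full adherence and no dropout. Time since first dose is then uniform from 168 to 168 + 7A days, in up to three bands:
- 168 to 350 days: mean O = 259, mean S = 259 − 7 + 70 = 322.
- 350 to 420 days: mean O = 385, S = 420.
- Above 420 days: S = O = 420.

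For A = 26 everyone is in the first band: 322/259 = 1.243. For A = 52 the bands are 182, 70 and 112 days wide. Mean S = (182×322 + 182×420)/364 = 371.0, mean O = (182×259 + 70×385 + 112×420)/364 = 332.8, and the ratio is 1.115. The share of subjects with unobserved days is 252/(7A), at most 100%.

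| Accrual A (weeks) | S/O | Rate too low by | Subjects with unobserved days |
|---|---|---|---|
| 26 | 1.243 | 19.6% | 100% |
| 52 | 1.115 | 10.3% | 69% |
| 78 | 1.070 | 6.6% | 46% |
| 104 | 1.051 | 4.8% | 35% |

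**The case against.** The strongest reply accepts the missing cap and disputes its weight.

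- **The largest figures are conditional.** The SAP does not say that rates per 100 patient-years will be produced at the Primary Analysis, and interim details sit in a separate unblinding plan that is not available here. This stands: the 5% to 20% range applies only if rates are run at that cut. The SAP does not restrict the rates to the final analysis either.
- **Arm comparisons are little affected at an early cut.** With concurrent randomization the understatement should be similar in every arm, and no test or threshold is attached to these rates. This also stands; the harm there is to absolute rates.
- **The final-analysis figures are near the upper end.** They assume a mean of 7 days between last dose and exit. With a mean gap of 28 days and the same mean last dose, leavers' mean O = 175 + 28 = 203, and the understatement is 1.0%, 2.2% and 3.4% at 10%, 20% and 30% loss. The 30% against 10% rate-ratio shift falls to about 2.4%. This is fair: it reduces the size without removing the bias.
- **A cap does not align everything.** A death found in public records after withdrawal, within 70 days of last dose, would count with no matching time. SAP 10.2.2 also asks for rates of deaths more than 70 days after last dose, which lie outside this denominator altogether. Both are true. The first should be rare, and the second is a separate mismatch in the opposite direction. Neither is a reason to keep unobserved time in the denominator.

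**Conclusion.** The concern holds. SAP 10.2.4 is complete and explicit, and it is wrong as written: followed literally, it counts time in which no event could be recorded. The direction is certain, because the added time can only lower the rate.

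The effect at the final analysis is small: roughly 1% to 5% on an arm's rate over the loss range examined, with rate-ratio shifts of 1.7% to 3.6% when loss differs by 10 to 20 percentage points and dosing continues until exit. It would be larger, about 5% to 20%, if rates were tabulated at the Primary Analysis. At the final analysis, completers and subjects who stop drug but remain in follow-up are unaffected. Percentages of subjects with events and the listings do not use this denominator.

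The absence of a cap and the direction are read directly from the documents. The magnitudes rest on assumed accrual, adherence and loss. The rule should be corrected, but the defect does not threaten the study's conclusions.

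**What to change.** In SAP 10.2.4, define the end of exposure as the earliest of last dose date plus 70 days, data cutoff date, date of death and end of study participation. Then subtract the first dose date. Apply this to every rate in 10.2.2, 10.2.4, 10.2.5 and 10.2.6.

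As a wording alignment only, state in SAP 10.2.1 that the 70-day window runs from the last dose of study drug, as Protocol 7.5 already does.

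The cost is two lines of SAP text and one minimum function in the exposure derivation, with no new data. Reported rates rise slightly wherever unobserved time had been counted.

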#### **10.2.5 SAEs (Including Deaths) and Adverse Events Leading to Study Drug Discontinuation**

SAEs (including deaths) and AEs leading to study drug discontinuation will be summarized by SOC and PT and in listing format.

In addition, the event rate per 100 patient-years of exposure will also be provided by SOC and PT for each treatment-emergent SAE and TEAE leading to study drug discontinuation.

#### **10.2.6 Adverse Events of Special Interest**

AESI will be summarized by SOC and PT and will be based on standardized or company MedDRA queries (SMQs or CMQs), or based on adjudication results. AESI to be summarized will follow those indicated in the latest version of the Product Safety Statistical Analysis Plan (PSSAP) for ABBV-154 in the AESI section. Detailed information about search criteria for the AESI are also provided in a table in the same section.

Tabular listings of AESI will be provided.

In addition, the event rate per 100 patient-years of exposure will also be provided by SOC and PT for each AESI.

### 10.3 Analysis of Laboratory Data

Data collected from central and local laboratories, including additional laboratory testing due to an SAE, will be used in all analyses, except for Baseline where SAE-related laboratory assessments on or before the first dose of study drug will be excluded. The clinical laboratory tests defined in the protocol operations manual (e.g., hematology and clinical chemistry) will be summarized.

Each laboratory variable will be summarized for all time points (starting with Baseline) with the number of non-missing observations, mean and standard deviation, median, minimum and maximum. Mean change from baseline to each applicable post-baseline visit will be summarized for selected laboratory variables, with the number of observations, baseline mean, and visit mean. The change from baseline mean, standard error, and 95% confidence interval will be presented for the mean change from baseline within each treatment group and difference between treatment groups (ABBV-154 vs. placebo).

Changes in laboratory parameters will be tabulated using shift tables either by NCI CTC criteria or categorized as low, normal, or high based on the normal ranges of the laboratory used for each sample. A shift table from baseline either to the worse value (based on NCI CTC criteria) during treatment or to minimum and maximum value (based on normal range), will be created. A similar shift table will be provided to summarize shifts from baseline to the final post-baseline value.

Laboratory abnormalities meeting CTC criteria grade 3 and 4 will be summarized.

Laboratory abnormalities will be evaluated based on Potentially Clinically Important (PCI) criteria (criteria in PSSAP will be used first, if the criteria are not available in PSSAP, then criteria in NCI CTC will be used). For each laboratory PCI criterion, the number and percentage of subjects who have a laboratory value meeting the criteria will be summarized. Listings will be provided to summarize subject-level laboratory data for subjects meeting PCI criteria.

For the purpose of assessing for potential Hy's law cases, the frequencies and percentages of subjects with post baseline liver specific function test values that meet the following criteria of potential clinical interest will be summarized by "as treated" treatment group:

- $ALT > 3 \times ULN$
- $ALT > 5 \times ULN$
- $ALT > 10 \times ULN$
- $ALT > 20 \times ULN$
- $AST > 3 \times ULN$
- $AST > 5 \times ULN$
- $AST > 10 \times ULN$
- $AST > 20 \times ULN$
- $TBL > 2 \times ULN$
- Alkaline phosphatase  $> 1.5 \times ULN$
- $ALT$  and/or  $AST > 3 \times ULN$  and concurrent  $INR > 1.5$
- $ALT$  and/or  $AST > 3 \times ULN$  and concurrent  $TBL > 2 \times ULN$

A listing of possible Hy's Law cases, defined as those who meet all of the following conditions simultaneously, will be provided:  $ALT > 3 \times ULN$  or  $AST > 3 \times ULN$  that is associated with an increase in bilirubin  $> 2 \times ULN$ .

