## 2.0 Study Design and Objectives

### 2.1 Objectives, Hypotheses and Estimands

The primary objective is to assess the safety and efficacy of ABBV-154 versus placebo in subjects with PMR, who are dependent on treatment with glucocorticoids with doses of at least 5 mg/day prednisone equivalent (glucocorticoid-dependent PMR).

- Primary Efficacy Objective: The primary efficacy objective of the study is to demonstrate that ABBV-154 treatment results in a longer disease-free time when compared with placebo treatment in the Intent-to-Treat (ITT) population, which consists of all randomized subjects with at least one dose of study drug.

The hypothesis corresponding to the primary efficacy objective is that the time to flare with ABBV-154 treatment is longer than that with placebo treatment. The estimand for

the primary endpoint is defined as the median time to flare in the study for each ABBV-154 group versus the placebo group in the ITT population. Subjects will be censored at the time of the last available assessment, initiation of immunomodulator, or violation of protocol-allowed systemic glucocorticoid use.

- Secondary Efficacy Objectives: The secondary efficacy objectives of the study are to demonstrate greater efficacy with ABBV-154 treatment when compared with placebo treatment with respect to the secondary endpoints specified in Section 3.3, in the ITT population.

The estimands corresponding to the secondary efficacy objectives are:

- For each binary secondary endpoint: The difference in percentage of subjects achieving a response for each ABBV-154 group versus the placebo group in the ITT population.
- For each continuous endpoint: The mean difference between each ABBV-154 group versus the placebo group in the ITT population.

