placebo. Note that measurements will be considered as missing after the start of confounding medication before MI. Regardless of MI imputed values, subjects after receiving confounding medication will be counted as non-responders.

Efficacy assessments after the initiation of rescue medication, immunomodulator or violation of protocol-allowed systemic glucocorticoid use will not be included in the analyses. As a result, the subjects will be considered as non-responders in the NRI-MI approach.

- **Mixed-Effect Model Repeat Measurement (MMRM):** MMRM will be the primary approach to the analysis of continuous variables except for glucocorticoid dose. The repeated measures analysis will be conducted using a mixed model including observed measurements at all visits. Subject's observations after intercurrent events will not be used in the MMRM. The mixed model includes the categorical fixed effects of treatment, visit and treatment-by-visit interaction, stratification factors at randomization [Glucocorticoid use at Baseline ( $\geq 10$  mg/day;  $< 10$  mg/day prednisone equivalent); Length of prior glucocorticoid treatment for PMR ( $\leq 1$  year;  $> 1$  year)], and the continuous fixed covariates of baseline measurement. An unstructured variance-covariance matrix (UN) will be used. If the model does not converge, an alternative variance-covariance structure matrix (e.g., autoregressive (1) or compound symmetry) will be used. Parameter estimation is based on the assumption of data being missing at random and the method of restricted maximum likelihood (REML) will be used.
- **Analysis of covariance (ANCOVA):** ANCOVA will be the primary approach for the analysis of glucocorticoid dose. No intercurrent event will be considered in the analysis of glucocorticoid dose. The ANCOVA model includes the categorical fixed effects of treatment and stratification factors at randomization [Glucocorticoid use at Baseline ( $\geq 10$  mg/day;  $< 10$  mg/day prednisone equivalent); Length of prior glucocorticoid treatment for PMR ( $\leq 1$  year;  $> 1$  year)], and baseline glucocorticoid dose as a covariate.
- **As Observed (AO):** The AO analysis will not impute values for missing evaluations, and thus a subject who does not have an evaluation on a scheduled

visit will be excluded from the AO analysis for that visit. AO will include all values collected in the study.

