#### **10.4 Analysis of Vital Signs**

Vital sign measurements of systolic and diastolic blood pressure, pulse rate, respiratory rate, and body temperature will be summarized.

Each vital sign variable will be summarized for all time points (starting with Baseline) with the number of non-missing observations, mean and standard deviation, median, minimum and maximum. Mean change from baseline to each applicable post-baseline visit will be summarized for each vital sign variable, with the number of observations, baseline mean, and visit mean. The change from baseline mean, standard error, and 95%

confidence interval will be presented for the mean change from baseline within each treatment group and difference between treatment groups (ABBV-154 vs. Placebo).

Vital sign variables will be evaluated based on PCI criteria. Pulse rate, body temperature, and respiratory rate will follow the criteria in Appendix B. All other vital sign measurements will follow criteria in PSSAP. For each vital sign PCI criterion, the number and percentage of subjects who have a vital sign value meeting the criteria will be summarized. Listings will be provided to summarize subject-level vital sign data for subjects meeting PCI criteria.

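### SAP 10.3 and 10.4 plan a CI for the between-arm difference in change from Baseline but name no model or covariate, so as written it is unadjusted: valid, but generally less precise than a Baseline-adjusted estimate

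*SAP*

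**What the plan says.** SAP 10.3 first describes within-arm summaries, the last of them being the average value at the visit: "Mean change from baseline to each applicable post-baseline visit will be summarized for selected laboratory variables, with the number of observations, baseline mean, and visit". It then commits to an interval: "The change from baseline mean, standard error, and 95% confidence interval will be presented for the mean change from baseline within each treatment group". The same sentence extends this to the "difference between treatment groups (ABBV-154 vs. placebo") contrast. SAP 10.4 repeats the commitment for each vital sign: "confidence interval will be presented for the mean change from baseline within each treatment group and difference between treatment groups (ABBV-154 vs. Placebo"). It lists systolic and diastolic blood pressure among those variables.

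Neither section names a model, a Baseline covariate or the stratification factors, and neither calls the difference raw or unadjusted. Both cite the Product Safety SAP, but only for potentially clinically important criteria. Protocol 7.5 adds only that "Mean change in laboratory and vital signs variables will be summarized" and leaves the details to the SAP.

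The continuous efficacy analyses are specified differently. In SAP 9.2.2, "MMRM will be the primary approach to the analysis of continuous variables except for glucocorticoid dose", with the Baseline measurement and two stratification factors in the model. Glucocorticoid dose is analyzed by ANCOVA with the same two factors "and baseline glucocorticoid dose as a covariate". Nothing extends these models to Section 10.

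**The concern.** Safety stands beside efficacy in the first objective (SAP 2.1: "The primary objective is to assess the safety and efficacy of ABBV-154 versus placebo"). The SAP chooses to report a between-arm contrast with an interval for these safety variables, so how it is estimated matters.

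A difference in mean change fixes the regression slope of the follow-up value on Baseline at 1. When the true slope is lower, the difference carries noise from chance Baseline imbalance that a Baseline-adjusted analysis removes. The covariate is already in hand: SAP 10.1 defines a safety Baseline, and the Activity Schedule collects vital signs, hematology and chemistry before treatment. At stake is the width of the intervals from which a reader would judge, for example, a blood pressure effect in arms of 40.

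**Working it through.** **The plan's own figures.** The documents give no SD, correlation or precision target for laboratory values or vital signs, so there is no stated figure to reproduce here. The one design calculation, in Protocol 7.10 and SAP 2.4, concerns flares. It reproduces: ln(0.70)/ln(0.30) = 0.296, and 37 events give 98.0% power by the Schoenfeld formula (95.1% by Freedman), consistent with more than 90%. This point does not affect it.

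**Inputs.** From SAP 2.4: 40 subjects per arm. Assumed: the Baseline-to-visit correlation rho, shown over 0.3 to 0.9, and equal SDs at Baseline and follow-up (relaxed below).

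**Formulas, equal variances.** Per subject, in units of SD²:
- change score variance: 2(1 − rho)
- residual variance after Baseline adjustment: 1 − rho²
- variance ratio: (1 − rho²) / [2(1 − rho)] = (1 + rho)/2
- large-sample CI width ratio: sqrt[(1 + rho)/2]

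The unadjusted half-width at 40 versus 40 is t(0.975, 78) × sqrt[2(1 − rho)] × sqrt(2/40). At rho 0.5 this is 1.99 × 1 × 0.2236 = 0.445 SD.

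A simulation at 40 versus 40 (2,000 runs per setting) adds the degrees of freedom and chance-imbalance cost of fitting the covariate:

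| rho | Unadjusted half-width (SD) | Formula width ratio | Simulated ratio, Baseline only | Narrower by about | Adjusted half-width (SD) |
|---|---|---|---|---|---|
| 0.3 | 0.527 | 0.806 | 0.813 | 19% | 0.527 × 0.813 = 0.428 |
| 0.5 | 0.445 | 0.866 | 0.872 | 13% | 0.445 × 0.872 = 0.388 |
| 0.7 | 0.345 | 0.922 | 0.929 | 7% | 0.345 × 0.929 = 0.321 |
| 0.8 | 0.282 | 0.949 | 0.956 | 4% | 0.282 × 0.956 = 0.270 |
| 0.9 | 0.199 | 0.975 | 0.981 | 2% | 0.199 × 0.981 = 0.195 |

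The simulated gain is gone at rho of about 0.97.

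**Unequal variances.** Let r be the follow-up SD divided by the Baseline SD. The change score variance is 1 + r² − 2·rho·r, and the adjusted residual variance is r²(1 − rho²). They differ by (1 − rho·r)², where rho·r is the regression slope. The gain is therefore never negative in large samples, and it vanishes when the slope is near 1. With rho 0.8 and r 1.2 the slope is 0.96, and the variances are 1.44 × 0.36 = 0.518 (adjusted) and 1 + 1.44 − 1.92 = 0.520 (unadjusted), so there is practically no gain.

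**Adding the two strata.** If they explain nothing beyond Baseline, the simulated width ratios at rho 0.3, 0.5, 0.7, 0.8 and 0.9 are 0.824, 0.884, 0.941, 0.969 and 0.994. That is about 1 percentage point worse than Baseline alone, and at rho 0.95 the ratio is 1.007, a slight loss. If the strata explain 5% of the residual variance, which is an assumption, the ratios are 0.802, 0.863, 0.917, 0.943 and 0.970.

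**The case against.** The strongest reply is that Section 10 is descriptive. The safety endpoints in SAP 3.4 are adverse events and potentially clinically significant values, not mean changes. Individual signals are sought through shift tables, grade 3 and 4 summaries, potentially clinically important counts, Hy's law criteria and adverse events of special interest. No test, margin or decision rule attaches to these intervals, so the efficacy models need not carry over. This limits the importance of the point but does not remove it: the SAP itself plans a between-arm difference with a 95% CI, and its precision depends on the method.

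It is also fair that the unadjusted reading comes from silence. If the sponsor intends an adjusted estimate, the method is simply unstated, and the same sentence cures that.

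A reader might infer more than the documents support:
- **That the planned CIs are wrong or biased.** They are not: under randomization the unadjusted difference is unbiased and its CI has its stated coverage.
- **That chance Baseline imbalance is a second harm on top of lost precision.** With 40 per arm, an imbalance at its own 95% limit is 1.96 × sqrt(2/40) = 0.44 SD, which moves the change difference by (1 − 0.5) × 0.44 = 0.22 SD at rho 0.5. But 2(1 − rho) − (1 − rho²) = (1 − rho)², so the extra variance is exactly this imbalance term. It is one effect, and the wider interval already covers it.
- **That power is lost.** No test is planned on these differences.
- **That glucose or HbA1c comparisons are affected.** SAP 10.3 limits mean change to selected variables and does not list them. HbA1c appears in the Activity Schedule and as a category in Appendix B, which does not place it among those selected. Blood pressure is named in SAP 10.4.
- **That omitting the strata widens the CIs.** Protocol 2.1 links glucocorticoid adverse effects to dose and treatment time, which makes a gain plausible, but the documents give nothing to show one.

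**Conclusion.** The point holds as a matter of specification and precision. As written, SAP 10.3 and 10.4 give an unadjusted between-arm difference in mean change from Baseline. It is valid but generally less precise than a Baseline-adjusted one.

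The size depends on quantities the documents do not give. With equal variances and 40 per arm, the saving in CI width runs from about 19% at rho 0.3 to about 2% at rho 0.9, and it is nil when the regression slope is near 1. A variable that tracks closely from Baseline to visit will gain little; one that fluctuates will gain more.

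This is a low-priority improvement to the safety tables. It does not bear on the flare analyses, on the counts and listings through which individual safety signals are sought, or on any decision rule.

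**What to change.** In SAP 10.3 and 10.4, state that at each visit the ABBV-154 versus placebo difference in change from Baseline, with its standard error and 95% CI, is estimated by ANCOVA with treatment and the Baseline value of that variable. The two analysis strata (glucocorticoid dose at Baseline, length of prior glucocorticoid treatment) may be added for consistency with the efficacy models, but should be treated as optional. Keep the observed within-arm means and mean changes as descriptive columns.

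The cost is one sentence in each section and a change of model in the table program, with no new data or subjects. One small downside: the adjusted difference will not equal the subtraction of the displayed raw means, so the tables need a footnote saying so.
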